## **OUTCOME MEASURES AND ENDPOINTS**

Outcome assessment time-points will be at the end of the 30-day baseline ( $\pm 2$  days), at the end of month 1 (day  $30 \pm 2$  days, the secondary end-point) and month 2 (day  $60 \pm 2$  days, the primary end-point) of the tDCS/sham intervention.

The primary comparison will be the between-group comparison at the end of month 2 of the tDCS/sham intervention.

**The primary outcome measure** will be *Change in mean number of migraine days per month.*

A note: A migraine day is defined as any calendar day on which the patient had onset, continuation, or recurrence of a migraine as recorded in the diary. A migraine is defined as a migraine (with or without aura) lasting at least 30 minutes. Any calendar day on which acute migraine medication is used is counted as a migraine day.

**Secondary outcome measures** will be:

1. *Percentage of responders*, determined as a number of patients having at least 50% reduction of monthly migraine days between the one-month baseline and post-intervention, in each of the two study groups;
2. *Change in monthly migraine attack frequency*,
3. *Change in monthly acute antimigraine drug use*,

all determined from the patients' diaries;

4. *Change in mean headache severity per migraine day* determined from Pain NRS ratings on migraine days;
5. *Change in quality of life* determined from ratings on the migraine-specific MSQ questionnaire;
6. *Change in depressive symptoms* determined from the Hamilton Depression Scale (HamD);
7. *Tolerability* determined from occurrence of side effects and adverse events related, probably related or possibly related to tDCS, through the study;
8. *Satisfaction* - percentage of patients stating at the end of the trial that they are very satisfied, moderately satisfied, or not satisfied with the treatment, determined from the 8-item tDCS User Survey at the end of the intervention;

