**Visit #2 - Familiarization with tDCS and Device Deployment** will be held either at the patient's home or at a designated room at the MJHS Institute, whichever is more convenient for the patient. Familiarization will build on tDCS information provided to the patient via flyer and tDCS booklet prior consenting. The study personnel will demonstrate the equipment and function of the device, instruct the patient on the use of the device, and will review the IRB-approved instructional booklet with the patient. The patient will have an opportunity to experience the sensory sensation associated with tDCS procedure by applying 30 seconds of tDCS stimulation on the arm at the intensity 1.5 mA that is planned be used in the study. The study personnel will also instruct the patient how to establish video connection for a remote contact with the tDCS supervising study personnel located at the MJHS Institute via a HIPAA-compliant Zoom application via the patient's phone, tablet or personal computer. (Patients who do not possess any of these electronic devices will be given an electronic Tablet equipped with Zoom capability for the study duration). At the end of Visit 2, the patient will carry-out the first tDCS/sham application under in-person supervision of study personnel.

**tDCS/Sham Applications in Home Settings.** After the first 20-minute tDCS/sham self-applied by the patient at Visit #2, the tDCS/sham self-applications will continue daily for the total of 60 days. Reminders will be sent by the study personnel via email and text message daily. In addition, study staff will be in regular remote contact with the patient via phone and/or HIPAA-compliant videoconferencing, at least three times per week during the first week and at least twice a week during the remaining weeks.

During the intervention period of the study, patients will continue keeping daily diaries, to document migraine occurrence, related symptoms and medication intake, as done at the baseline period. Patients will receive reminders about the diaries via email and text messages. The diaries will be in electronic form and patients will be sent the diaries to the study site once a week via encrypted HIPAA-compliant email or by fax.

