process data - number of delivered applications and the protocol fidelity in each study group will be analyzed, in order to support evidence on feasibility of the procedure.

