#### Monitoring of Subjects and Criteria for Withdrawal of Subjects

**Adverse Events (AEs):** Study personnel will monitor study participants for AEs thorough the course of the study, and in 30-day post-study safety follow-up by phone.

Any AE that is ongoing at the time of the participant's study completion or withdrawal will be followed by the study physician and PI until the event resolves or stabilizes.

AEs will be captured, by the Investigator or designee, in the subject's source documents and on the case report form (CRF). AEs will be followed by the study physician and Principal Investigator and reported to the IRB in accordance with regulatory requirements.

Fluctuation of intensity and frequency of symptoms evaluated in the study is expected due to natural course of the chronic illness. If the patient reports significant worsening of any symptom during treatment, this will be conveyed to the study physician, who will assess the patient's report and offer the patient appropriate follow-up.

The participant may withdraw from the study at any point for any reason.

Participants may be removed from the study for the following reasons:

- Not following the study protocol or instructions from study personnel.
- Participants who during familiarization (Visit 2) find the sensory sensation associated with the stimulation unacceptable.
- Participants who after instruction are not able to perform tDCS in accordance with the procedure described in the patient's instructional booklet.

- If a serious adverse event related or potentially related to the study procedure occurs.
- If the study closes.

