## Analysis Plan (Update 1.29.20)

Participants will be randomized within randomly selected blocks of sizes 2, 4, and 6. The randomization list will be generated by an investigator not otherwise associated with the administration of treatment or collection of data.

All patient characteristics and outcomes will be evaluated for distribution. For all bivariate tests, the appropriate parametric or non-parametric test will be selected based on distribution. Patient characteristics will be described and bivariate tests will evaluate any differences across treatment group (active tDCS vs. sham tDCS). Primary and secondary outcomes at baseline will be described and bivariate tests will evaluate any differences across group. Bivariate tests will evaluate differences in attrition, patient satisfaction, adverse events (including all adverse events, serious adverse events, and adverse events attributed to the treatment), and quality of blinding across group.

All outcomes will be described using data visualization. Differences in outcome between the active tDCS and sham tDCS groups will be evaluated in both intent-to-treat and completer analysis using non-parametric statistics as appropriate (see Table below). Intent-to-treat analysis will impute missing values using all available data. Differences in outcome between people with chronic (15 or more headache days/month) vs. episodic migraine, with and without medication overuse (e.g., using a MSM on 10 or more days per month during the baseline period), and with high and low levels of patient compliance will also be evaluated using the appropriate non-parametric statistic.

Alpha will be set at 0.05, two-tailed, for all analyses. SPSS v. 25.0 and R will be used for all analyses.

Primary Outcome	Description	Tentative Analysis Type
Change in migraine day/30 day	Median change in the number of migraine days per 30 day period, from M0 to M2.	Mann-Whitney U
Secondary Outcomes		
Responders	% of participants who report a 50% reduction in migraine days, from M0 to M2.	Fisher's Exact Test
Change in headache attack/30 days	Median change in number of attacks per 30 day period, from M0 to M2.	Mann-Whitney U
Change in acute medication use	Median change in number of days on which an acute medication was used from M0 to M2.	Mann-Whitney U
Change in headache attack intensity	Median change in NRS from headache days in a 30 day period from M0 to M2.	Mann-Whitney U

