Change in Migraine-Specific Quality of Life – Total, and 3 subscales	Median change in MSQ score from M0 to M2	Mann-Whitney U
Change in Hamilton Depression Scale	Median change in Ham-D score from M0 to M2	Mann-Whitney U
Tolerability	Side effects AEs Total AEs related in any degree to the treatment	Mann Whitney Us
Satisfaction	% of participants who report being satisfied with the treatment	Fisher's Exact Test

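### The tolerability row states no unit or exposure basis and omits stopping for side effects, so early stoppers can rank as tolerating the device better than completers

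*SAP*

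**What the plan says.** The protocol (Outcome Measures and Endpoints) defines tolerability by the "occurrence of side effects and adverse events related, probably related or possibly related to tDCS, through the study". It does not say whether that is a count, an incidence or a rate.

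The table in the SAP (Analysis Plan, Update 1.29.20) lists side effects, adverse events and "AEs related in any degree to the treatment", with "Mann Whitney Us" as the method, in a column headed "Tentative Analysis Type". No denominator, severity grading or discontinuation component appears. The SAP text adds bivariate comparisons of attrition and of all, serious and treatment-attributed adverse events. It also plans a completer analysis and a general rule that the intention-to-treat analysis imputes missing values.

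On exposure, the protocol says that "the tDCS/sham self-applications will continue daily for the total of 60 days" (Study Procedures and Methods) and that safety calls run for 30 days after the last application. The withdrawal section lets participants leave at any time and lists grounds on which they may be removed, among them: "If a serious adverse event related or potentially related to the study procedure occurs". The "number of delivered applications" is to be analysed in each group (Sample Size and Data Analysis), but as evidence of feasibility, with no link to tolerability.

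**The concern.** Safety is named in Aim 1 alongside efficacy, and tolerability is its listed outcome. A count of events grows with the number of sessions and days observed, and both can be cut short by the events themselves. A patient who gives up after a few sessions because of side effects then contributes a small count, which a rank test reads as good tolerability. If the active arm loses more patients this way, its counts fall just when tolerability is worse. The error then runs towards a conclusion of good tolerability. As written, the plan never reports how many patients stopped because of side effects.

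**Working it through.** **Figures in the plan.** There is none for tolerability. The only sample size figure, 26 per arm, rests on responder rates and has no bearing here. All event rates and stopping shares below are assumptions, because the documents give none.

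**1. Is a count meant?** The same SAP table assigns Fisher's exact test to both outcomes expressed as a percentage of participants (responders, satisfaction). Using Mann-Whitney for tolerability therefore points to a number per patient. This is an inference, since no unit is stated.

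**2. Unequal observation.** A completer has 60 sessions and about 60 + 30 = 90 days of adverse event observation. A patient stopping at session 5 has 5 sessions and about 5 + 30 = 35 days.

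**3. Two patients.** Patient A has 2 events in 5 sessions: 2/5 = 0.40 per session. Patient B has 4 mild events in 60 sessions: 4/60 = 0.067 per session. A's rate is 6 times B's, yet A's count is lower, so A ranks as the better tolerator.

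**4. How often does that ranking occur?** Take Poisson counts, with a completer mean of 4 and a stopper at session 5 whose rate is m times the completer's. The stopper's mean is 4 × m × 5/60, and P(stopper has fewer) = Σk P(stopper = k) × P(completer > k).

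| m | stopper mean | P(stopper has fewer) |
|---|---|---|
| 1 | 0.33 | 95% |
| 3 | 1 | 88% |
| 6 | 2 | 73% |
| 12 | 4 | 43% |

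The break-even rate ratio is 60/5 = 12. With a completer mean of 1, the four probabilities are 60%, 55%, 47% and 35%.

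These figures include stoppers with no event. A patient who stops because of a side effect has at least one. With exactly one event, that patient has fewer than a completer who has two or more:
- completer mean 4: 1 − e⁻⁴(1 + 4) = 91%
- completer mean 1: 1 − e⁻¹(1 + 1) = 26%

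So the misranking is likely when events are frequent and much less so when they are rare.

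**5. Effect on the comparison.** Simulated trials used 30 per arm and 60 sessions, with per-session event probability = (arm mean/60) × a gamma(1,1) patient factor. Means were 4 (active) and 2 (sham), with a two-sided 5% Mann-Whitney test on counts. Each setting had at least 3,000 trials, so the simulation error is at most √(0.5 × 0.5/3000) = 0.9 percentage points. Stopping shares are patients who would stop if the trigger event occurs. About 1/(1 + 4) = 20% of active patients have no event, so shares of 15% and 30% mean roughly 12% and 24% actually stop at a first event.

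| Stopping pattern | Active shown as worse: 0% | 15% | 30% |
|---|---|---|---|
| Active only, at first event | 51% | 30% | 15% |
| Active only, after third event | 51% | about 43% | about 40% |
| Equal in both arms, at first event | 51% | about 39% | about 34% |

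With equal event rates (4 and 4) and 30% stopping in the active arm only, active is declared significantly better in about 19% of trials. The nominal chance in that direction is 2.5%.

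**6. A second model.** With 26 per arm, Poisson counts, sham mean 4, active rate 1.5 times higher and active stoppers leaving at session 5, raw counts show active as worse in 87%, 57%, 24% and 7% of trials for 0%, 10%, 20% and 30% stopping. Events per session give 87%, 94%, 98% and over 99%. Those last figures flatter the rate, because each stopper was given at least one event in 5 sessions. With equal rates and 20% stopping, raw counts show active as significantly better in about 20% of trials.

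**7. Does another part of the plan repair this?** The attrition comparison is not split by cause. The serious-event comparison does not capture stopping for non-serious side effects. The completer analysis drops the early stoppers. The imputation rule does not say whether or how event counts after stopping are imputed.

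**The case against.** The strongest reply is that the row is tentative and states no unit, so nobody has committed to raw counts, and that the SAP already compares attrition and serious events between arms. This stands in part. Counts are the natural reading but not the stated one, and stopping does not go unexamined. What is missing is stopping by cause.

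A reader might also infer that the worst tolerators always receive the best ranks. The documents do not support that. A patient with a related serious event has a count of at least 1, removal is permitted but not required, and monitoring continues for 30 days. A stopper with 5 events in 5 sessions ranks worse than a completer with 4.

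Nor do removals of those who "find the sensory sensation associated with the stimulation unacceptable" show poor tolerance of active treatment. That rule applies at Visit 2 familiarization, where the 30-second arm stimulation is the same for both groups and comes before the first assigned application.

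Finally, the large losses need stopping to be unequal and prompt. The documents give no stopping rate, and the protocol's background cites good acceptability in longer protocols.

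**Conclusion.** The point holds in conditional form. The tolerability row lacks a unit and an exposure basis and omits stopping because of side effects. If per-patient counts are used and active patients stop more often, the comparison is diluted, and it can reverse. Under the assumptions in the working, detection falls from about 51% to as low as 15% with prompt active-only stopping at a 30% share. It falls only to about 34% to 43% with equal or later stopping. The false finding of better tolerability is about 19% in the equal-rate case with 30% active-only stopping. These sizes illustrate the mechanism and do not forecast this trial.

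It would go too far to say that the plan definitely tests raw counts, that early stoppers necessarily rank best, or that worst-rank scoring is the cure. When 30% stop in both arms, worst-rank detects 29% against 34% for raw counts and 43% for events per session. This is a secondary safety outcome and the change is cheap, so it should be made.

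**What to change.** In the SAP's tolerability row:

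1. Add the number of patients in each arm who stop or are removed, after starting assigned treatment, because of a side effect or adverse event. Give an exact 95% confidence interval for the difference.
2. Add the number in each arm with at least one related event, with the same interval. This cannot stand alone: in the simulation it detects the doubled rate only about 15% of the time.
3. Keep the count comparison, but state its unit and express it per delivered session or per day observed, using the session data already collected. Read it beside item 1, because stopping at an event inflates that patient's rate.
4. Report Visit 2 familiarization removals separately, because they precede assigned treatment.
5. Use worst-rank scoring, if at all, only as a sensitivity analysis.

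The cost is SAP wording and one coded field for the reason for stopping. That reason must be classified before unblinding.
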